**2. Induction**

**2.1 Phase I (fixed dose of idarubicin of 10 mg/m^2 day 1-3 and cytarabine 1 g/m^2 day 1-5)**

Clofarabine IV over approximately 1 hour daily for 5 days (days 1-5). Dose levels and dose escalation schema are described below.

Idarubicin 10 mg/m^2 IV over approximately 30 minutes daily for 3 days (days 1-3)

Cytarabine 1 g/m^2 IV over approximately 2 hours daily for 5 days (days 1-5)

Idarubicin will follow clofarabine by 1 to 2 hours and cytarabine will follow clofarabine by 3 to 6 hours. All chemotherapeutic agents will be dosed, prepared, and administered according to MDACC institutional guidelines. BSA will be recalculated prior to each subsequent course.

Patients will be entered sequentially to each dose level. If none of the first 3 patients at a dose level experience first cycle dose-limiting toxicity (DLT), new patients may be entered at the next higher dose level. If 1 of 3 patients experience first cycle DLT, up to 3 more patients are started at that same dose level. If 2 or more experience first cycle DLT, no further patients are started at that dose and clofarabine's dose will be reduced to -1 level, which is 10 mg/m^2 IV daily for 5 days. The MTD is the highest dose level in which <2 patients of 6 develop first cycle DLT. New dose levels may begin accrual only if all patients at the current dose level have been observed for a minimum of 4 weeks.

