## 2.2 Phase II

In the Phase II portion, patients will randomized to receive

a. Clofarabine (dose selected based on Phase I portion) IV over approximately 1 hour daily for 5 days (days 1-5)

b. Idarubicin  $10 \text{ mg/m}^2$  IV over approximately 30 minutes daily for 3 days (days 1-3)

c. Cytarabine  $1 \text{ g/m}^2$  IV over approximately 2 hours daily for 5 days (days 1-5)

Idarubicin will follow clofarabine by 1 to 2 hours and cytarabine will follow clofarabine by 3 to 6 hours.

**or**

a. Fludarabine  $30 \text{ mg/m}^2$  IV over approximately 30 minutes daily for 5 days (days 1-5)

b. Idarubicin  $10 \text{ mg/m}^2$  IV over approximately 30 minutes daily for 3 days (days 1-3)

c. Cytarabine  $1 \text{ g/m}^2$  IV over approximately 2 hours daily for 5 days (days 1-5)

Idarubicin will follow fludarabine by 1 to 2 hours and cytarabine will follow fludarabine by 3 to 6 hours.

The induction or reinduction may be given over 4 days (Fludarabine, Clofarabine and Cytarabine) in patients  $\geq 65$  years, or at the discretion of the treating physician and over 3 days (Fludarabine, Clofarabine and Cytarabine) in patients with PS  $\geq 2$ , or at the discretion of the treating physician. Idarubicin  $8\text{-}10 \text{ mg/m}^2$  will be given for 2 days in these situations.

Patients, who have not achieved a complete remission following one induction course can receive a second induction course to optimize response if possible. A second induction course at the same dose as the previous course or in a dose-reduced fashion

should not be given until at least 28 days of course 1. If the bone marrow aspirate and/or biopsy(s) performed after the re-induction cycle reveals a remission marrow (CR/CRp), then the patient may proceed with consolidation at the discretion of the treating investigator. In addition, any clinically significant drug-related, non-hematologic toxicity experienced by a patient should return to  $\leq$  grade 2 or the baseline grade before the patient continues treatment. Should the patient not have achieved a remission after the reinduction course, he will be taken off study for failure to respond, unless the patient has achieved clinical benefit or partial remission, at which time further therapy on protocol may be permitted with approval from the PI.

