### **Consolidation**

Patients in CR or CRp can continue with up to 6 consolidation cycles.

Clofarabine (dose selected based on Phase I portion) IV over approximately 1 hour daily for 3 days (days 1-3)

Idarubicin 8 mg/m^2 IV over approximately 30 minutes daily for 2 days (days 1-2)

Cytarabine 1 g/m^2 IV over approximately 2 hours daily for 3 days (days 1-3)Or

Fludarabine 30 mg/m^2 IV over approximately 30 minutes daily for 3 days (days 1-3)

Idarubicin 8 mg/m^2 IV over approximately 30 minutes daily for 2 days (days 1-2)

Cytarabine 1 g/m^2 IV over approximately 2 hours daily for 3 days (days 1-3)

The consolidation may be given over 2 days in patients  $\geq$  65 years and/or with PS  $\geq$  2.

Cycles may be repeated every 3 to 10 weeks based on leukemia response and resolution of drug-related toxicities. Prior to each consolidation cycle, the ANC should be  $\geq 1.0 \times 10^9/L$ , and the platelet count should be  $\geq 60 \times 10^9/L$  (except for patients who are considered to have achieved a CRp following induction/reinduction and in whom the platelet count may be lower). Patients with borderline values for ANC and platelet count (value up to 10% lower than recommended) can still proceed with the next consolidation cycle if this is judged to be in the best interest of the patients and after discussion with the principal investigator. In addition, any drug-related non-hematologic toxicity experienced by the patient must return to  $\leq$  grade 2 before receiving the next cycle. Doses missed or held during a cycle of treatment will not be made up and are recorded as being omitted. If patients experience multiple study drug-related toxicities or experience significant infections, dose adjustments may need to be made based on the most severe toxicity and based on the drug causing the toxicity.

Dose modifications:

Drug doses in subsequent consolidation cycles may be modified for drug-related  $>$  grade 2 non-hematologic toxicities. Dose reductions can also be made in other clinical situations where this step is considered to be in the best interest for the patient and after discussion with the principal investigator. The following table is a suggestion for dose modifications in subsequent treatment courses:

Dose level	Fludarabine (mg/m  )	Clofarabine (mg/m  )	Idarubicin (mg/m  )	Cytarabine (g/m  )
-1	22.5	15	8	0.75
-2	20	15	6	0.5

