-3	15	10	6	0.25
----	----	----	---	------

Doses of each individual drug can be modified if a toxicity is considered due this particular drug.

Specific Dose Modifications for Organ Function:

	Fludarabine (mg/m  )	Cytarabine (g/m  )	Idarubicin (mg/m  )	Clofarabine (mg/m  )
Creatinine (mg/dL)				
2.1 – 3 (age < 65)	22.5	0.75	10 * 8 **	75% of current dose level
2.1 – 3 (age ≥ 65)	15	0.5	8 * 6 **	50% of current dose level
Above 3	Discuss with study principal investigator			
Bilirubin (mg/dL)				
2.6 – 5	30	1	5 * 4 **	Current dose level
Above 5	30	1	OMIT	Current dose level

\*Induction/Re-Induction

\*\*Consolidation

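### The suggested dose-modification table does not fit the plan's own doses: idarubicin level -1 equals full consolidation dosing in both arms, and the fixed clofarabine levels are reductions only if phase I selects more than 15 mg/m2

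*Combined protocol and SAP*

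**What the plan says.** **Clofarabine dose.** Section 2.1 (Phase I) lists levels of 10 (level -1), 15 (starting), 20, 25 and 30 mg/m2. After two or more first-cycle DLTs, the "dose will be reduced to -1 level, which is 10 mg/m"2. The dose carried forward is defined by rule: "The MTD is the highest dose level in which <2 patients of 6 develop first cycle DLT". Section 2.2 (Phase II) gives induction as "Clofarabine (dose selected based on Phase I portion) IV over approximately 1 hour daily for 5 days (days 1-5"), and the Consolidation section uses the same selected dose: "Clofarabine (dose selected based on Phase I portion) IV over approximately 1 hour daily for 3 days (days 1-3").

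**Idarubicin dose.** Induction is 10 mg/m2, or 8-10 mg/m2 in the shortened schedules (section 2.2). Consolidation is 8 mg/m2 in both arms.

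**Dose-modification table.** Its scope is set by "Drug doses in subsequent consolidation cycles may be modified for drug-related" non-hematologic toxicity above grade 2, and it is presented as follows: "The following table is a suggestion for dose modifications in subsequent treatment courses". For levels -1, -2 and -3 the entries are:
- fludarabine 22.5, 20, 15 mg/m2
- clofarabine 15, 15, 10 mg/m2
- idarubicin 8, 6, 6 mg/m2
- cytarabine 0.75, 0.5, 0.25 g/m2

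The line after the table allows one drug to be modified alone when the toxicity is attributed to it.

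**Organ-function table.** The next table is built differently. For raised creatinine, clofarabine is scaled to what the patient is receiving (for example "75% of current dose level" for patients under 65). Idarubicin has separate induction and consolidation values.

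**The concern.** A negative dose level is normally read as a step down from the full dose. Here some steps have no effect, and under one possible phase I outcome two of them would be a step up. A clinician who applied level -1 after a significant toxicity in consolidation could record an idarubicin reduction while giving the same dose. With clofarabine the result depends on a phase I outcome that was unknown when the fixed table was written. Up to six consolidation cycles are allowed, so the table may be used more than once in a patient. Recorded dose levels would then be a poor description of treatment given, and the safety profile of the two regimens is a secondary endpoint.

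**Working it through.** The plan states no figure to reproduce. The check compares each table entry with each full dose that the plan allows, taking both as daily doses in the same units.

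**Formula.** Percent change = 100 x (table dose / full dose - 1).

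**Inputs.** Full doses: clofarabine 10, 15, 20, 25 or 30 mg/m2 (section 2.1; carried forward in section 2.2 and Consolidation); idarubicin 8 mg/m2 in consolidation and 10 mg/m2 in standard induction; fludarabine 30 mg/m2; cytarabine 1 g/m2. Table doses are those listed above.

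**Results.**

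| Drug, full dose | Level -1 | Level -2 | Level -3 |
|---|---|---|---|
| Idarubicin 8 (consolidation) | 8/8: 0% | 6/8: -25% | 6/8: -25% |
| Idarubicin 10 (induction) | 8/10: -20% | 6/10: -40% | 6/10: -40% |
| Clofarabine 10 | 15/10: +50% | 15/10: +50% | 10/10: 0% |
| Clofarabine 15 | 15/15: 0% | 15/15: 0% | 10/15: -33% |
| Clofarabine 20 | 15/20: -25% | 15/20: -25% | 10/20: -50% |
| Clofarabine 25 | 15/25: -40% | 15/25: -40% | 10/25: -60% |
| Clofarabine 30 | 15/30: -50% | 15/30: -50% | 10/30: -67% |
| Fludarabine 30 | 22.5/30: -25% | 20/30: -33% | 15/30: -50% |
| Cytarabine 1 | 0.75/1: -25% | 0.5/1: -50% | 0.25/1: -75% |

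**Reading the table.**
1. Whatever phase I selects, idarubicin level -1 changes nothing in consolidation, in either arm. It is a 20% reduction only from the 10 mg/m2 induction dose. From 8 mg/m2, the lower end of the shortened induction range, it is again 0%.
2. Whatever phase I selects, clofarabine does not move from level -1 to -2, and idarubicin does not move from -2 to -3. If one drug is adjusted alone, those steps are empty.
3. Depending on phase I, clofarabine levels -1 and -2 leave the dose unchanged if 15 is selected and raise it by half if 10 is selected. At 20, 25 or 30 every level is below the full dose.
4. Fludarabine and cytarabine fall at every level.

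**The case against.** The strongest defence is that the table is only advisory. It is worded as a suggestion, and the sentence before it says that doses may be modified. It is also not the only guidance after a toxicity above grade 2, as a reader might infer. The Consolidation section requires drug-related non-hematologic toxicity to recover to grade 2 or less before the next cycle, lets adjustments follow the worst toxicity and the drug responsible, and allows other reductions after discussion with the principal investigator. A separate table covers creatinine and bilirubin. This stands, and it limits the severity. It does not make an empty step coherent: those provisions say when to re-treat and who may decide, and outside organ function this table is where stepwise doses are given.

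Second, the lead-in to the table refers to subsequent treatment courses, which could include re-induction, and section 2.2 allows a dose-reduced second induction. There idarubicin 10 to 8 is a reduction. That reading is possible, but the table sits under Consolidation, its opening sentence concerns consolidation cycles, and it must work there too.

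Third, repeated entries are not in themselves a contradiction in a ladder for several drugs. From -1 to -2 clofarabine holds while the other three columns fall, and from -2 to -3 idarubicin holds while the others fall. This stands when all drugs move together. It does not help when one drug is changed alone.

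Two stronger readings are tempting and not supported. One is that the problem affects only the experimental drug and so biases the comparison of arms. The no-change step that holds unconditionally is idarubicin, which is the same in both arms. Only the clofarabine entries are specific to CIA, and nothing in the documents sizes an effect on the comparison. The other is that the protocol instructs clinicians to raise clofarabine after toxicity. The increase arises only if 10 mg/m2, a level below the starting dose, is selected, and the surrounding text speaks of reductions.

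**Conclusion.** The point holds as an internal inconsistency that should be corrected. Unconditionally, idarubicin level -1 is a 0% change in consolidation in both arms, and two steps (clofarabine -1 to -2, idarubicin -2 to -3) are empty when a single drug is modified. Conditionally, clofarabine levels -1 and -2 change the dose by +50%, 0%, -25%, -40% or -50% for a selected dose of 10, 15, 20, 25 or 30 mg/m2. This rests on reading the table entries as daily doses and on all five phase I levels being possible selections, as section 2.1 is written. The documents do not state the selected dose, so they do not show that any patient would be given more clofarabine after a toxicity. Because the table is advisory and leaves room for judgement, the severity is moderate.

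**What to change.** The sponsor should reconcile the dose-modification table with the phase I dose levels in section 2.1, the induction doses in section 2.2 and the consolidation doses, and should state whether the table covers re-induction as well as consolidation. The adjacent organ-function table already treats clofarabine and idarubicin differently, so the two tables should be reviewed together. Which doses and modification rules apply is for the investigators to set; this review proposes none. The cost is one table corrected by amendment. No change to sample size, randomization or analysis follows from it.

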**V. PRETREATMENT AND POST-TREATMENT EVALUATION**

**Induction Treatment (Pre-treatment)**

1. CBC, diff, platelet count.
2. Creatinine, bilirubin, ALT or AST, marrow aspirate with cytogenetics (if bone marrow not done within 1 month or cytogenetics within 3 months. For patients with evidence of leukemia in the peripheral blood, the bone marrow may be omitted after discussion and approval with the principal investigator.)

Pretreatment Evaluation

Procedure	Comments	Schedule
Informed Consent	Obtain standard informed consent approved by IRB	Within 14 days of therapy
Medical History	History of present illness, known allergies, prior cancer history as far as traceable, and past medical/ surgical history as far as relevant.	Within 14 days of therapy
Physical Examination	Vital signs (temperature, heart rate, respiratory rate, blood pressure) and performance status.	Within 14 days of therapy
Concomitant	Document concomitant medications	Within 14 days

Procedure	Comments	Schedule
Medications		of therapy
Hematology	CBC with differential and platelet count	Within 14 days of therapy
Biochemistry	Creatinine, total bilirubin, SGPT or SGOT	Within 14 days of therapy
Bone marrow	Aspirate and/or biopsy Cytogenetics	Within 30 days of therapy Within 90 days of therapy
Pregnancy test	Serum or urine, if female and of child-bearing potential only	Within 7 days of therapy

- For patients with evidence of leukemia in the peripheral blood, the bone marrow may be omitted after discussion and approval with the PI.

### During therapy

1. CBC, differential, and platelet count every 3-7 days (the differential may be omitted when the WBC is  $\leq 500$ .)
2. Creatinine, bilirubin, ALT or AST once weekly.
3. Marrow aspirate to confirm complete remission.

### During Therapy

Procedure	Comments	Schedule
Hematology	CBC with differential and platelet count	Every 3-7 days (the differential may be omitted when WBC is $\leq 500$ )
Biochemistry	Creatinine, total bilirubin, SGPT or SGOT	Once weekly
Physical Examination	Focused physical examination	Prior to each treatment course
Bone marrow	Aspirate and/or biopsy	On day 28 +/- 7 days

### During Post-Remission Therapy

CBC, diff, platelet count, creatinine, and bilirubin prior to each post-CR course. Marrow aspirates every 2-3 cycles.

## **Targeted Therapy**

Patients with AML may harbor FLT3/ITD mutations. We have previously explored the use of sorafenib in these patients and was found to be safe and therefore we can allow patients with FLT3/ITD mutations to receive concomitant sorafenib therapy at a dose of 400 mg orally twice daily continuously at the discretion of the treating physician.

In addition patients with Acute Myeloid Leukemia may evolve from Myeloid Fibrosis where JAK2 inhibitors such as ruxolitinib was found to be effective therefore we will allow the concomitant use of ruxolitinib @ 20 mg BID at the discretion of the treating physician.

Patients with the presence of BCR/Abl or the Philadelphia chromosome may receive concomitant therapy with any approved TKI. TKI therapy will be given orally and should be given continuously. The choice and the dose will be at the discretion of the investigator.

## **Supportive care**

Supportive measures such as prophylaxis for tumor lysis syndrome, erythropoietin, analgesics, blood transfusions, antimicrobials and hematopoietic colony stimulating factors for treatment of cytopenias are permitted. The administration of anti-leukemia therapies is not permitted, except for hydroxyurea which is allowed for up to 7 days each during cycle 1-3 and the use of a single or a two day dose of cytarabine (up to 3 g/m^2) for emergency use up to 24 hours prior to start of study therapy. Intrathecal chemotherapy is allowed for patients with CNS disease.

## **VI. STUDY END POINTS**

### **Primary:**

1. Complete remission rates with the 2 different regimens

### **Secondary:**

1. Event free survival at 2 years (events defined as death and relapses)

2. Overall survival
3. Remission duration
4. Predictive factors for response and outcome
5. Safety profile

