**Secondary:**

Evaluate the durability of response, the overall and event-free survival rates, and the safety profile of 2 different regimens.

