## **VII. CRITERIA FOR WITHDRAWAL**

Reasons for withdrawal include:

- withdrawal of consent or the subject refuses to continue treatment and/or procedures/observations.
- relapse unless the treating physician determines that the patient has achieved clinical benefit, at which time further therapy on protocol may be permitted with approval from the PI.
- failure to achieve at least a CRi after 2 induction courses

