**Relapse:**

Increase of bone marrow blasts to  $> 10\%$  after an initial response.

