### **Phase II**

The phase II portion of the study will include only newly diagnostic AML patients, and the primary objective is to compare the event-free survival (EFS) between treatment CIA and FLAI, where event is defined as be resistance to treatment, relapse (after response) or death, whichever occurred first.

A maximum of 200 front-line patients will be enrolled in the study. To enroll 200 front line patients, the total sample size (front-line and salvage patients combined) is 280.

This section will focus on front-line patients only. An adaptive randomization algorithm will be used to assign the patients to the two treatment arms. Initially 40 patients will be randomized equally to the two treatment arms. After the completion of the equal randomization, the adaptive randomization algorithm will be employed to unbalance the

randomization probabilities in favor of the treatment arm with a better event free survival. The expected accrual rate is about 5 patients per month, and the additional follow-up time is 12 months after all patients have been enrolled to the study.

The historical data suggested the median event free survival time for FLAI treatment was 5 months. Let  $\theta_1$  and  $\theta_2$  denote the median event free survival time for treatment arm CIA and FLAI respectively, we assume the prior for the median event free survival time follows Inverse Gamma (IG) distribution:  $\theta_1 \sim \text{IG}(3, 10)$ , and  $\theta_2 \sim \text{IG}(3, 10)$ . Each time a new patient enters the trial, be the posterior probabilities  $\pi_i = \Pr(\theta_i > \theta_j \mid \text{data})$  will be calculated ( $i, j = 1, 2$ ). The randomization probability to treatment arm CIA and FLAI will be the posterior probabilities  $\pi_i = \frac{\sqrt{\pi_i}}{\sqrt{\pi_1} + \sqrt{\pi_2}}$ .

The trial will be stopped early for both efficacy and futility based on the follow stopping rules. Table 1 presents the operating characteristics of simulations based on the described design.

1. Early loser selection: Suspend accrual to an arm  $i$  if  $\Pr(\theta_i < \theta_{j \neq i} \mid \text{Data}) < 0.025$
2. Early winner selection: Stop the trial and select an arm  $i$  as superior if  $\Pr(\theta_i > \theta_{j \neq i} \mid \text{Data}) > 0.975$
- 3 Final winner selection: At the final analysis after all patients have been evaluated, select arm  $i$  as superior if  $\Pr(\theta_i > \theta_{j \neq i} \mid \text{Data}) > 0.975$

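### The secondary 2-year EFS in Section VI omits resistance, which the EFS in Section X counts as an event, so two different endpoints carry one name

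*Combined protocol and SAP*

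**What the plan says.** Section VI (Study End Points, Secondary) lists "Event free survival at 2 years (events defined as death and relapses". The Phase II part of Section X (Statistical Considerations) states that "the primary objective is to compare the event-free survival (EFS) between treatment CIA and FLAI". For that comparison it names three kinds of event, one more than Section VI does: "resistance to treatment, relapse (after response) or death, whichever occurred first". The same part of Section X bases adaptive randomization, early stopping and final selection on that EFS.

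Three other places bear on the difference:

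- **Relapse (Section VIII).** It is defined as "Increase of bone marrow blasts to" more than 10%, and only in a patient who has first responded.
- **Non-responders in the treatment plan (Section 2.2, Phase II).** Of a patient still not in remission after reinduction, the text says "he will be taken off study for failure to respond". It makes an exception, with PI approval, for clinical benefit or partial remission.
- **Withdrawal (Section VII).** One reason is "failure to achieve at least a CRi after 2 induction courses". No exception is attached to that reason.

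The Analysis method paragraphs analyse EFS without restating its events. Nothing in the documents says that two EFS endpoints are intended, and nothing defines or dates resistance as an event.

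**The concern.** Resistance cannot be read into the word relapse in Section VI, because the protocol's own definition of relapse needs a prior response. A patient who goes through induction without any response therefore has an event at resistance under Section X. Under Section VI the same patient stays event-free until death.

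Such patients are not rare in the background figures. The Rationale gives CR rates of 50-60% for fludarabine/cytarabine-containing regimens in newly diagnosed disease, and 70% and 83% for two arms of an anthracycline trial. Both regimens here are induction regimens, so failure to remit is one of the main outcomes on which they could differ.

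At stake is the meaning of the reported 2-year EFS. Read as written, it would not be the 2-year value of the EFS curve that decides the trial, and a reader would have no reason to suspect that.

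**Working it through.** **1. Event lists side by side**

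| Patient | Section X | Section VI |
|---|---|---|
| Responds, then relapses | event at relapse | event at relapse |
| Dies in induction or in remission | event at death | event at death |
| Never responds, dies later | event at resistance | event at death |

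Only the last row differs. A patient with partial response only is a grey case: Section VIII does not say whether the initial response in the relapse definition must be CR or CRi.

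**2. The plan's own figure**

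Table 1 was checked by simulating the Section X design, with 2000 trials per scenario. Event times were exponential and the posterior for each median was IG(3 + events, 10 + ln 2 × exposure). The first 40 patients were randomized equally, then by square-root weights, with the 0.975 rule, a maximum of 200 patients, 5 per month and 12 months of further follow-up.

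| True medians (months) | Pr(Selected), Table 1 | Simulated |
|---|---|---|
| 5 v 5 | 0.12 / 0.111 | 0.115 / 0.125 |
| 2 v 5 | 0 / 1 | 0 / 1 |
| 7 v 5 | 0.757 / 0.014 | 0.746 / 0.014 |
| 8 v 5 | 0.937 / 0.001 | 0.931 / 0.004 |
| 10 v 5 | 0.995 / 0.001 | 0.997 / 0.001 |

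Table 1 reproduces within 2 points, so the discrepancy is not an arithmetic fault in the design.

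**3. Size of the difference**

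The documents do not give the inputs needed, so these are assumptions: CR at month 1; 12-month median from CR to relapse or death; resistance declared at month 2; median survival m after resistance of 3 to 6 months; induction death not modelled. The CR rate c is 60%, 70% or 83%, from the Rationale.

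- Responders: R(t) = 2^(−(t−1)/12) after month 1. R(24) = 2^(−23/12) = 0.265 and R(2) = 2^(−1/12) = 0.944.
- Resistant patients, alive: N(t) = 2^(−(t−2)/m) after month 2. N(24) = 0.006 for m = 3 and 0.079 for m = 6.
- Section X: S(t) = c·R(t) after month 2. The median is 1 + 12·log2(2c).
- Section VI, followed to death: S(t) = c·R(t) + (1−c)·N(t).
- Section VI, resistant patients censored at month 2: S(t) = [c·R(2) + (1−c)]·R(t)/R(2).

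Two-year EFS:

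| CR | Section X | Section VI, to death (m = 3 to 6) | Difference | Section VI, censored | Difference |
|---|---|---|---|---|---|
| 60% | 15.9% | 16.1-19.0% | 0.2-3.1 | 27.1% | 11.2 |
| 70% | 18.5% | 18.7-20.9% | 0.2-2.4 | 27.0% | 8.4 |
| 83% | 22.0% | 22.1-23.3% | 0.1-1.3 | 26.8% | 4.8 |

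For example, at 60%: 0.60 × 0.265 = 0.159. Adding 0.40 × 0.079 = 0.031 gives 0.190.

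Median EFS in months:

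| CR | Section X | Section VI, to death | Difference |
|---|---|---|---|
| 60% | 4.2 | 8.0-10.4 | 3.9-6.2 |
| 70% | 6.8 | 9.0-11.0 | 2.2-4.1 |
| 83% | 9.8 | 10.6-11.8 | 0.8-2.0 |

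**4. Sensitivity, anchored to the 5-month FLAI median in Section X**

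This takes 60% CR, 8% induction death (the Rationale's figure, from relapsed/refractory patients), 32% resistant and scored at month 1 or 2, and m of 4 to 8 months. The responders' median is set at 15.4 months so that the Section X median is 5. The Section VI median is then 8.9-12.0 months, and 2-year EFS is 21% under Section X against 22-26% under Section VI.

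**The case against.** The strongest reply is that the decision rules are not ambiguous. Section X states its own event list in the Phase II text that sets the comparison, the randomization and the stopping rules, and nothing applies the Section VI list there. That stands. A reader might infer that the conflict alters the chance of selecting CIA. Simulation can be made to show this: if CIA raised CR from 60% to 75%, selection falls from about 0.53 to 0.22-0.35 when Section VI events are fed into the algorithm. But the protocol never feeds them in, so that is not a consequence of the plan.

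A second reply is that the effect at 2 years, the time point Section VI names, is small. This also stands for follow-up to death, because most resistant patients would have died by then. Under Section VI, death after resistance is counted late rather than left out.

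A reader might also infer that a gain in remission rate would vanish from the Section VI endpoint. In the censored column a rise in CR from 60% to 83% does leave 2-year EFS at about 27%. That requires censoring at removal from study. Sections 2.2 and VII speak of leaving study or withdrawal, not of censoring, and overall survival in the same endpoint list implies follow-up to death. With such follow-up the contrast remains: 6.1 points under Section X (15.9% to 22.0%) and about 4-6 points under Section VI.

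Finally, the numerical inputs are assumed, and the 70% and 83% CR rates come from other regimens in patients aged 50 to 70. This limits the size of the effect but leaves the two event lists in conflict.

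**Conclusion.** The documents contain two EFS event lists that differ on resistance, and nothing reconciles them. This is an internal inconsistency confined to the secondary 2-year EFS. It should be fixed, but it does not undermine the decision rules or Table 1.

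Under the assumptions of step 3, with follow-up to death, the two definitions differ by about 0-3 points at 2 years and about 1-6 months in the median. The anchored sensitivity, with longer survival after resistance, gives at most about 5 points (21% against 26%) and about 4-7 months. The gap of about 5-11 points at 2 years depends on a censoring rule that the documents neither state nor exclude.

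That the conflict exists rests on the text alone; only its size rests on assumptions. Which endpoint is primary, and whether 12 months of further follow-up supports a 2-year estimate, are separate questions.

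**What to change.** 1. In Section VI, replace the parenthesis with the Section X event list ("resistance to treatment, relapse (after response) or death, whichever occurred first") and use it for every EFS analysis: allocation, stopping, the median and the 2-year value.
2. State, for analysis purposes, what counts as resistance and on which date the event falls. Copying the Section X words alone would import an undefined term. The analysis definition must be reconciled with Section 2.2, which has an exception for clinical benefit or partial remission, and with Section VII, whose withdrawal criterion has none. This concerns the analysis only, not how such patients are treated.
3. State that patients taken off study for failure to respond are not censored for EFS.
4. If a death-or-relapse endpoint is still wanted, restrict it to responders and call it relapse-free survival.

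The cost is a short wording amendment: the event list, a dated definition of resistance and a censoring sentence. The reported 2-year EFS becomes slightly less favourable.
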